12.0 Descriptive Factors

- 12.1 Rai Stage: 0 vs. 1 vs. 2 vs. 3 vs. 4. (Appendix II)
- 12.2 CD38⁺ expression: Positive ($\geq 30\%$) vs. negative ($< 30\%$).
- 12.3 Chromosomal anomalies as detected by FISH: 13q- vs. 12+ vs. 11q- vs. 17p- vs. other abnormality vs. normal karyotype.
- 12.4 IgV_H mutation status: Mutated ($\geq 2\%$) vs. unmutated ($< 2\%$) vs. indeterminate.
- 12.5 ZAP-70 expression: Positive ($\geq 20\%$) vs. negative ($< 20\%$).

13.0 Treatment/Follow-up Decision at Evaluation of Patient

- 13.1 If the patient develops PD at any time during active treatment they will go to event monitoring. If the patient develops unacceptable adverse events, if the treating physician feels it is in the patient's best interest, or if the patient refuses all further study participation, study treatment will be discontinued, and the patient will go directly to event monitoring. Patients will then be followed in event monitoring per Section 18.0.
- 13.2 Patients not progressing on active treatment will continue treatment per protocol up to a maximum of 36 cycles. After the completion of 36 cycles, the patient will go to observation (maximum duration of observation 2 years). After completing observation, patients will enter event monitoring. NOTE: Patients who have residual disease at the end of 36 cycles will continue to event monitoring.
- 13.3 A patient is deemed ineligible if after registration, it is determined that at the time of registration, the patient did not satisfy each and every eligibility criteria for study entry. The patient may continue treatment off-protocol at the discretion of the physician as long as there are no safety concerns and as long as the patient was properly registered. The patient will go directly to the event-monitoring phase of the study (or off study, if applicable).
 - If the patient received treatment, all data up until the point of confirmation of ineligibility must be submitted. Event monitoring will be required per Section 18.0 of the protocol.
 - If the patient never received treatment, on-study material and the End of Active Treatment/Cancel Notification Form must be submitted. No further data submission is necessary.

Note: Due to the nature of the disease, if the patient is diagnosed with DLBCL within the first cycle of treatment, it will be assumed that the DLBCL was present at registration. The patient will be deemed ineligible per Sec 3.27.

- 13.4 A patient is deemed *cancel* if he/she is removed from the study for any reason before any study treatment is given. On-study material and the End of Active Treatment/Cancel Notification Form must be submitted. No further data submission is necessary.

13.5 If a patient develops DLBCL at any time, it will be considered progressive disease. The patient will go directly to the event monitoring phase of the study per Section 18.0. If the patient develops any other hematological malignancy while on study, it will not be considered progressive disease.

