- 16.323 Time to requirement of next therapy: A landmark analysis will be conducted to evaluate time to requirement of next therapy for patients who achieve a confirmed MRD-negative response in both the blood and bone marrow vs. those who remain MRD-positive, as assessed at 48 weeks (end of 12 cycles; +/- 4 weeks). Patients who discontinue treatment before 48 weeks are excluded from this analysis. Time to requirement of next therapy will be defined as the time from the 48 week MRD evaluation until the time of initiation of subsequent treatment for progressive CLL. The distribution of time to requirement of next therapy will be estimated using the Kaplan-Meier method and log-rank statistics will be utilized to evaluate differences between the two groups.
- 16.324 Progression-free survival: A landmark analysis will be conducted to evaluate progression-free survival for patients who achieve a confirmed

MRD-negative response in both the blood and bone marrow vs. those who remain MRD-positive, as assessed at 48 weeks (end of 12 cycles; +/- 4 weeks). Patients who discontinue treatment before 48 weeks are excluded from this analysis. Progression-free survival will be defined as the time from the 48 week MRD evaluation until the time of disease progression per the IWCLL criteria or death due to any cause. The distribution of progression-free survival will be estimated using the Kaplan-Meier method and log-rank statistics will be utilized to evaluate differences between the two groups.

16.325 Adverse Events: Platelets and hemoglobin will be graded according to the Grading Scale for Hematologic Adverse Events in CLL Studies in Appendix V. The maximum grade for each type of adverse event, regardless of causality, will be recorded and reported for each patient, and frequency tables will be reviewed to determine adverse event patterns. Adverse events will continue to be recorded and reported up to 30 days after the last day of study drug treatment.

16.33 Correlative Analyses. The reports on the correlative will be descriptive as they are exploratory in nature.

16.332 Study of the impact of ibrutinib treatment on mood is exploratory in nature. Reports of these correlative analyses will be descriptive.

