16.35 Data & Safety Monitoring

16.351 The principal investigator(s) and the study statistician will review the study at least every quarter to identify accrual, adverse events, and any endpoint problems that might be developing. The Mayo Clinic Cancer Center (MCCC) Data Safety Monitoring Board (DSMB) is responsible for reviewing accrual and safety data for this trial at least twice a year, based on reports provided by the MCCC Statistical Office.

16.352 Adverse Event Stopping Rule: The stopping rule specified below is based on the knowledge available at study development. We note that the rule may be adjusted in the event of either (1) the study re-opening to accrual or (2) at any time during the conduct of the trial and in consideration of newly acquired information regarding the adverse event profile of the treatments under investigation. The study team may choose to suspend accrual because of unexpected adverse event profiles that have not crossed the specified rule below.

Accrual will be temporarily suspended to this study if at any time we observe events considered at least possibly related to study treatment (e.g., an adverse event with attribute specified as "possible," "probable," or "definite") that satisfy either of the following:

- If 3 or more of the first 12 treated patients experience a grade 4 or higher non-hematologic adverse event at least possibly related to treatment.
- If after the first 12 patients have been treated, 25% of all patients experience a grade 4 or higher non-hematologic adverse event at least possibly related to treatment.

We note that we will review grade 4 and 5 adverse events deemed "unrelated" or "unlikely to be related," to verify their attribution and to monitor the emergence of a previously unrecognized treatment-related adverse event.

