| CRF | Event Monitoring Phase ¹ | | | | |
|------------------|---|--|--|-------|--------------------|
| | q. 3 months until PD or subsequent treatment for CLL ² | At PD or subsequent treatment for CLL ² | q. 6 mos. after PD or subsequent treatment for CLL | Death | New Primary |
| Event Monitoring | X | X | X | X | At each occurrence |

1. If a patient is still alive 5 years after registration, no further follow-up is required.
2. Submit copy of documentation of progression to the Operations Office, Attention: QAS for MC1481, [contact].

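### For treated patients later found ineligible, 13.3 ends required data at confirmation of ineligibility, so some non-serious toxicity can be missing from the 16.325 tables and, occasionally, from the 16.352 count

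*Combined protocol and SAP*

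**What the plan says.** Section 13.3 covers patients found, after registration, not to have met the entry criteria. For those already treated it says "If the patient received treatment, all data up until the point of confirmation of ineligibility must be submitted", followed by "Event monitoring will be required per Section 18.0 of the protocol". The patient goes directly to event monitoring, or off study where applicable. Exposure need not end there: "The patient may continue treatment off-protocol at the discretion of the physician as long as there are no safety concerns".

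The event-monitoring table in 18.1 lists a single form. It is due "q. 3 months until PD or subsequent treatment for CLL", then at and after that point, at death, and at a new primary cancer. The Nadir/Adverse Event form and the ADR/AER row appear only in the active-monitoring table.

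The safety analysis is framed by patient and by exposure, not by eligibility. Section 16.325 says "The maximum grade for each type of adverse event, regardless of causality, will be recorded and reported for each patient" and "Adverse events will continue to be recorded and reported up to 30 days after the last day of study drug treatment". The first limb of the stopping rule in 16.352 reads "If 3 or more of the first 12 treated patients experience a grade 4 or higher non-hematologic adverse event", restricted to events at least possibly related to treatment. After the first 12, the rule uses 25% of all patients. Neither section excludes ineligible patients.

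**The concern.** Eligibility is a sound reason to leave a patient out of the efficacy denominator, as 16.11 does. It is no reason to shorten toxicity follow-up for a drug the patient has already taken. Under 13.3 as written, the patient stays among the treated while part of the 30-day window may go uncollected. The maximum grade in the 16.325 tables, and the numerator in 16.352, can then only be too low.

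The situation can arise by the plan's own rules. A note in 13.3 makes a patient diagnosed with DLBCL during the first treatment cycle ineligible after dosing has begun. The data cut-off then falls within weeks of first exposure.

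**Working it through.** **Step 1: what is retained and what can be lost.** Take an event after confirmation of ineligibility and within 30 days of the last study dose.

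| Event | Route that survives 13.3 | Consequence |
|---|---|---|
| Serious, any attribution | Expedited under 10.4, with no eligibility condition; also routine data under 10.1(f) | Retained |
| Death | Expedited under 10.52 | Retained |
| Major hemorrhage, serious or not | Reported on SAE timelines under 10.41 | Retained in safety reporting |
| Related grade 2; non-serious grade 3 | 10.62 asks for them, but 13.3 has set a cut-off and 18.1 lists no form for the phase | Can be missing from 16.325 |
| Related grade 3 or 4 blood-count events named in 10.43 | Exempt from expedited reporting, so routine forms only | Can be missing from 16.325; not counted in 16.352 |
| Related grade 4 non-hematologic, not serious | As for grade 2 and 3 | Can be missing from 16.325 and 16.352 |

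The last row exists because the stopping rule works by grade, and 10.1 itself warns that severe and serious are different. An isolated laboratory value is the obvious example. Events before confirmation are submitted and counted in every row.

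**Step 2: how many patients.** Section 16.22 allows 3 extra registrations, out of 35, for ineligibility, cancellation, major violation and other reasons together: 3/35 = 8.6%. Cancelled patients are never treated (13.4), so treated ineligible patients are only part of the 3. Even if all 3 were of this kind, the pro rata number among the first 12 is 3 × 12/35 = 1.03, or about one.

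**Step 3: a ceiling for the stopping rule.** The documents give no operating characteristics for 16.352, so there is no stated figure to reproduce. (The efficacy table in 16.24 does reproduce, at 0.0738, 0.3997, 0.7279 and 0.9069, and this point does not affect it.) With n patients whose events are seen and true rate p,

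P(X ≥ 3) = 1 − Σ C(n,k) p^k (1−p)^(n−k), summed over k = 0, 1, 2.

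At p = 0.25:

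- n = 12: 1 − (0.0317 + 0.1267 + 0.2323) = 0.6093
- n = 11: 1 − (0.0422 + 0.1549 + 0.2581) = 0.5448

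| Assumed true rate | All 12 seen | One patient's events wholly lost | Fall |
|---|---|---|---|
| 0.10 | 0.1109 | 0.0896 | 0.0213 |
| 0.20 | 0.4417 | 0.3826 | 0.0591 |
| 0.25 | 0.6093 | 0.5448 | 0.0645 |
| 0.30 | 0.7472 | 0.6873 | 0.0599 |

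The rates are assumptions; the documents give none for related grade 4 or higher non-hematologic events in this setting. Setting n = 11 discards every event in one patient. Under the plan only the last row of the Step 1 table is at risk for 16.352, and only after confirmation, so the real fall is smaller than any figure shown.

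**The case against.** A reader might infer that 13.3 stops data submission and that related toxicity in these patients drops out of the stopping count. The documents do not support that.

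- Section 10.4 requires every serious event within 30 days of the last administration to be reported, and later ones if related. It sets no eligibility condition.
- The exemptions in 10.43 are all hematologic, so no event that counts toward 16.352 is exempt.
- Section 10.1(f) requires expedited events to enter the routine data as well. Most related grade 4 and 5 non-hematologic events therefore still reach the count.
- The 13.3 bullet can be read as a minimum. The release from further data submission is written only for patients who were never treated.
- Patients who stop for progression or toxicity under 13.1 also go to event monitoring, so the move alone does not cancel the 30-day window.
- Section 10.7 refers late events to a Forms Packet that is not among the documents and may cover some of this.
- Treatment continued under 13.3 is described as off-protocol, so when the 30-day clock in 16.325 starts is arguably ambiguous rather than in flat conflict.

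All of this narrows the point, but it does not remove it. Section 13.1 sets no data cut-off, whereas 13.3 does, and a site could reasonably stop adverse event forms on reading it. Section 10.1(f) points to Sections 10.6 and 18.0 for routine submission, yet 18.1 lists no adverse event form for event monitoring. An unclear last-dose date is itself a reason to state one.

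A reader might also suppose that ineligible patients carry higher toxicity risk. The documents give no figure for this, and the point does not need it.

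**Conclusion.** The inconsistency is real and its effect is small. Section 13.3 does not fit the 30-day, per-patient adverse event reporting in 16.325 or the treated-patient basis of 16.352. The exposed events are those without an expedited route after confirmation. In the 16.325 tables these are chiefly related grade 2 and non-serious grade 3 events. In the 16.352 count they are the occasional non-serious grade 4 non-hematologic event.

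The number of patients is limited by the planning allowance of 3 in 35 for all such losses. That is an expectation, not a cap. The direction is fixed: anything missed lowers reported toxicity. The fall from 0.609 to 0.545 is an upper bound for one patient, at an assumed rate, with all of that patient's events lost; it should not be read as the expected effect. The primary endpoint, sample size, significance level and power are untouched. This is a cheap improvement, not a threat to the trial's conclusions.

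**What to change.** - **13.3, bullet for treated patients:** require all data up to confirmation of ineligibility and, in addition, the adverse event forms under 10.6 until 30 days after the last dose of study-supplied ibrutinib. Naming study-supplied drug fixes the end of the window when treatment continues off-protocol.
- **16.325 and 16.352:** state that the safety set is every patient who received at least one dose, whatever the eligibility status.
- **Efficacy denominator in 16.11 and 16.311:** leave as it is.

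The cost is one sentence in 13.3 and one in each of the two statistical sections. The only downside is continued use of an existing form for a few patients. The change concerns data collection only and takes no position on whether such patients should continue treatment.

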14.0 Body Fluid Biospecimens

14.1 Summary Table of Research Blood and Body Fluid Specimens to be Collected for this Protocol

| Correlative Study (Section for more information) | Mandatory or Optional | Blood or Body Fluid being Collected | Type of Collection Tube (color of tube top) | Volume to collect per tube (# of tubes to be collected) | Visit 1:Baseline (pre-tx) Visit 2: Prior to Cycle 4 Visit 3: Prior to Cycle 7 Visit 4: Prior to Cycle 13 Visit 5: At time of relapse | Process at site? (Yes or No) | Temperature Conditions for Storage /Shipping |
|--|--------------------------|---|---|---|--|------------------------------------|---|
| WES studies and Mate-pair DNA sequencing | Mandatory | Blood | EDTA | 5 mL (2) | X | YES | Ambient |
| | | Bone marrow | | 5 mL (2) | X ¹ | | |
| BTK signalosome analysis only for patients with MRD+ disease in blood and/or marrow ² | Mandatory | Blood | Heparin (green top) | 5 mL (2) | X | YES | Ambient |
| | | Bone marrow | | 5 mL (2) | X ¹ | | |
| Immunomodulatory effect analysis | Mandatory | Blood | Heparin (green top) | 6 mL (1) | X | YES | Ambient |
| | | Bone marrow | | 6 mL (1) | X ¹ | | |

1. Only if bone marrow biopsy or aspirate is done as part of routine clinical care of the patient or as part of MRD assessment.

2. Sample should also be collected at the time of first documentation of lymphocytosis >5,000cell/mm³.

14.2 Collection and Processing

All samples will be collected and stored at [name] laboratory ([name]; [contact]).

14.3 Rationale and Methodology

14.3.1 Determine the molecular profile predictive of eradication of CLL clone by ibrutinib

Scientific rationale: The current molecular landscape in CLL biology is able to identify patients with high vs. low risk disease in context with standard therapeutics, such as chemoimmunotherapy. However, recent data on ibrutinib seem to demonstrate that the clinical response to ibrutinib is independent of the traditional risk factors such as del(17p). This suggests that molecular markers currently employed may display a differential sensitivity to ibrutinib therapy. Furthermore, certain del(17p) patients upon relapse demonstrate a more aggressive clinical path than other del(17p) patients, hinting at underlying molecular architecture that is directing clinical responsiveness (or lack thereof) to ibrutinib. In this study we expect that ibrutinib treatment of the MRD will result in abrogation of the microenvironmental signaling through the BTK pathway and thus be able to eliminate residual clone. However, we do not expect all patients to be able eradicate MRD with ibrutinib, and this is consistent with the differential clinical response noted in prior studies (21% CR only).

Hypothesis: Therefore, our hypothesis is that it is the primary molecular makeup that directs responsiveness of the malignant clone to BTK inhibition by ibrutinib and that the extent of sensitivity of the clone will be predictive of ability to achieve an MRD-negative disease state.

Methodology & Sample: to address this, we will perform whole genome sequencing and mate-pair DNA sequencing of the malignant clone obtained from patient's blood (2 x 5ml tubes) and / or bone marrow (when available 2 x 5ml tubes). CD19+ cells will be sorted and used for WES. B-CLL cells are known to have two types of mutations: small (site mutations) and large (genomic rearrangements such as translocations, inversions, etc.), and the combination of mate-pair sequencing and WES will enable the detection of both types of lesions. A time series study is ideal for studying clonal evolution, which plays an important role in CLL. This will allow the identification of the sub-clone(s) in the MRD+ patients that were able to survive / eradicate with ibrutinib therapy. The protocol requires to have normal control DNA. This control DNA can be obtained from any one of the samples (which ever is convenient to the patient and preferred by the treating MD). Establishing whether molecular architecture is associated with response or lack of response to ibrutinib therapy will also be attempted by in silico predictive modeling simulation techniques, as previously described (Cellworks Inc.) For this analysis, blinded and de-identified data will be used to derive response from the in silico modeling algorithm. Control: It is important to have controls, which will represent lack of response to ibrutinib (or other anti-CLL therapeutics) to help design in silico algorithms. For this we will collect peripheral blood (2 x 5mL tubes) and/ or bone marrow (when available 2

x 5mL tubes) as well as buccal swab from CLL patients who are not enrolled on trial (and thus not on maintenance therapy for MRD eradication), but who have received ibrutinib with suboptimal clinical response. Possible sources for this DNA identified include either one of the following: 1. buccal swabs, 2. myeloid cells in the marrow (in cases where bone marrow is obtained for clinical reasons) or 3. Skin biopsy (if no other source of germline DNA is available).

Statistical support: WES analysis will be done at Mayo Clinic laboratories, and the data will be analyzed in collaboration with [name], PhD.

Sample time: sample will be collected any time prior to starting the ibrutinib therapy and then at time of relapse. Additional samples during treatment will be collected as noted in Table 14.1.

Expected results: This data will help us identify (a) unique molecular patterns of Clone that correlates with highest sensitivity of response to ibrutinib maintenance therapy and achievement of MRD negativity (b) molecular makeup of CLL clone associated with the most expeditious eradication of MRD vs. delayed eradication vs. persistent MRD and (c) molecular profile of the CLL clone associated with the longest durability of MRD negativity and (d) assess for clonal evolution and alteration of molecular profile of the CLL clone post exposure/resistance to ibrutinib therapy.

Clinical implications: these analyses will allow us to determine which patients are exquisitely sensitive to eradication of disease from ibrutinib maintenance therapy and thus will benefit from continued ibrutinib therapy and allow the identification of patients who may harbor a clone that would increase the potential of relapse or development of resistance to ibrutinib maintenance therapy, and thus require more frequent monitoring or perhaps timely use of additional therapeutic(s) to prevent development of ibrutinib resistance.

14.32 **Determine the role of members of the BTK signalosome in eradication of CLL clone by ibrutinib**

Scientific Rationale: It is evident from the clinical data^{53,54} that over 70% of the patients will respond to ibrutinib therapy; however, 80% of these "clinically responsive" patients will retain the CLL clone, while approximately 20% will go into CR. This variability in the depth of clinical response may suggest an underlying adaptability of the CLL clone's mediation through components of the BTK signalosome. Woyach et al reported⁵⁵ that CLL patients treated with ibrutinib demonstrated upregulation of p-Akt and p-Erk (downstream mediators of BTK) in some (but not all) patients and suggest that these downstream pathways may contribute to the survival of these CLL cells.⁵⁶ They also concluded that these cells may not be dependent upon the proximal BTK pathways mediated apoptosis and thus resistant to killing by ibrutinib. While this phenomenon is primarily reported in the displaced CLL cells, we ask the question of whether these pathways play any role in inability to eradicate the disease altogether from the bone marrow?

Hypothesis: Depth of response (i.e., eradication of the MRD) is dependent on the viability of the downstream mediator of the BTK pathway and its response to ibrutinib exposure.

Methodology & Sample: to address this question we will establish the profile of BTK signalosome for each patient through determination of the mRNA (RT-PCR/ nanostring assay) and protein expression (western blot analysis) of members of the BTK signaling pathway. Validation of BTK signaling, and the predictive ability of BTK (and other signaling pathways) for therapy response / or lack of response will be attempted through in silico modeling using a previously published (REF) platform (Cellworks Inc.). For this analysis, blinded and de-identified data will be used to derive response from the in silico modeling algorithm.

Samples: Blood (2 x 5ml green top tubes) and/or bone marrow samples (when available 2 x 5ml green top tubes) will be collected at anytime prior to initiating the ibrutinib therapy. Serial blood samples (first at the time of first documentation of lymphocytosis $>5,000\text{cell/mm}^3$ and then prior to starting cycles 4, 7, and 13 and then at time of relapse) will be collected if patients are noted to have lymphocytosis as a result of ibrutinib therapy. Bone marrow samples will only be collected when the procedure is performed as part of the clinical care of the patient and will follow the bone marrow biopsy and aspirate schedule noted in section 4. Control: It is important to have controls, which will represent lack of response to ibrutinib (or other CLL therapeutics) to help design in silico algorithms. For this we will collect peripheral blood (2 x 5mL tubes) and/ or bone marrow (when available 2 x5mL tubes) as well as buccal swab from CLL patients who are not enrolled on trial (and thus not on maintenance therapy for MRD eradication), but who have received ibrutinib with suboptimal clinical response.

Expected results: We anticipate (a) a variability in the expression and phosphorylation status of various members of the BTK pathway (Syk, Lyn CD79 FYN) and their targets (ERK, AKT, NFKB and Bcl-2, Mcl-1, XIAP, MYC, CD40 and CFLAR) (b) and predict a correlation of this variability with the ability to eradicate the MRD.

14.33 **Determine the contribution of immunomodulatory effects of ibrutinib in eradication of MRD and maintenance of clinical response**

Scientific rationale: our prior investigation of lenalidomide in CLL demonstrated that while lenalidomide was not directly cytotoxic it mediated its anti-CLL effect through activation of an innate (NK cell dependent) coupled by a CD8+ cytotoxic immune response. This resulted in 18% of the patients achieving MRD-negative disease with lenalidomide alone. Thus immune restoration can effectively deliver deeper responses in CLL. Traditional induction regimen incorporates chemoimmunotherapy (such as fludarabine and cyclophosphamide) causing direct insult to host immunity. Interestingly, many patients demonstrate regeneration of T cell enrich lymphocytic nodules in the bone marrow. In cancer redirection of host immunity from a predominant Th2 to Th1 response can deliver antitumor response. Dubovsky et al⁵⁷ recently reported in an elegant paper that ibrutinib can bind to ITK (IL-2 inducible kinase). ITK a member of the TEC-kinase family mediate TCR signaling through PLC γ , NFAT, NF κ B and MAPK. This results in activation and proliferation of CD8+ cells. We wonder

whether the eradication of MRD in CLL is perhaps *also* dependent upon its immunomodulatory effects.

Hypothesis: Ibrutinib alters the Th2:Th1 balance in the blood and bone marrow microenvironment, skewing towards a more Th1 profile, and this translates into its effects on the MRD. We further hypothesize that the robustness of the Th1 response will direct ibrutinib's depth of response i.e., MRD negativity post-induction.

Method and samples: Blood and/or bone marrow will be evaluated/quantified for Th1 and Th2 cells by flow cytometry. Changes in the cellular profile as well as respective cytokine levels (such as IL2, IL12, INF α and IL4, IL5, IL13 and IL10, respectively) will be measured (for cytokines we will use a multiplex assay). Blood (1 x 5ml green top tubes) and/or bone marrow samples (when available, 1 x 5ml green top tubes) will be collected at anytime prior to initiating the ibrutinib therapy. Serial blood samples (starting at 0 month and then every 3 cycles at time of MRD/clinical response assessment and then at time of relapse) will be collected. Control samples will be collected from CLL patients who are not enrolled on trial (not on maintenance therapy for MRD eradication), but who received ibrutinib and achieved suboptimal clinical response. Peripheral blood (2 x 5mL tubes) and/ or bone marrow (when available 2 x5mL tubes) as well as buccal swabs will be collected. *Note that the bone marrow sample will only be collected when the procedure is being done for clinical reasons* and will follow the bone marrow biopsy and aspirate schedule noted in section 4. Changes in cytokine levels will also be implemented into the in silico predictive simulation modeling algorithm and resulting effect on tumor cell proliferation as well as correlation with response to therapy will be assessed. Expected results: We anticipate that ibrutinib treatment (a) will result in an increase in Th1 cells both in the blood and the bone marrow with bone marrow demonstrating a higher percentage of Th1 cell activity and that (b) extent of immune cellular response will correlate with the robustness of the MRD eradication and that (c) the cytokine profile will mimic this cellular pattern and can be used to predict immune cellular response to ibrutinib.

Clinical relevance: CLL patients have been reported to have immune dysfunction or restoration of host immunity and immune cellular function with drugs such as lenalidomide, but to date there is no approved agent to address this aspect of CLL therapy. Identification / validation of immune restoration ability of ibrutinib and its correlation with disease eradication in the maintenance setting will be a highly novel observation and will define a unique role and mechanism of ibrutinib in CLL.

